### **3.9.1 Procedures for discontinuation of a patient from investigational product**

At any time, patients are free to discontinue investigational product or withdraw from the study (i.e., investigational product and assessments – see Section 3.10), without prejudice to

---

 Patient is considered lost to follow up when any of the following attempts of contact are failed: -3 attempts of either phone calls, faxes or emails; - having sent 1 registered letter/certified mail; 1 unsuccessful effort to check the vital status of the patient using publicly available sources, if allowed by local regulations.

further treatment. A patient that decides to discontinue investigational drug will always be asked about the reason(s) and the presence of any adverse events. If possible, they will be seen and assessed by an Investigator(s). Reasons for premature discontinuation of IP should be recorded in the eCRF.

All patients who prematurely discontinue IP should return to the study centre and complete the procedures described for the Premature IP Discontinuation visit (IPD) within 8 weeks +7 days after the last dose of IP. At that visit, patients should be encouraged to remain in the study to complete all subsequent study visits, procedures and assessments or alternatively agree to be contacted by phone calls at monthly intervals in order to collect AEs/SAEs, changes in concomitant medication, health care utilisation, and asthma exacerbation information.

If a patient is withdrawn from study, see Section 3.10. Patients not willing to continue to participate in the study should return to the study centre 1 last time within 16 weeks ±7 days after the last dose of IP for final study related assessments, ePRO devices if applicable (e.g., for patient reported outcomes) and all study drugs should be returned by the patient. Any AEs that are unresolved at the end of study will be followed up by the Investigator for as long as medically indicated, but without further recording in the CRF (See Section 6).

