Patients will return the ePRO device on EOT or IPD visit (for patients who are not willing to continue to participation in the study).

Completion or early termination of the treatment will be registered via IWRS/IVRS for each patient.

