#### **8.4.1.4 Forced expiratory volume in 1 second**

Pre-bronchodilator FEV1 is a key secondary efficacy endpoint of this study, and the change from baseline to Week 48 is included in the testing strategy.

The change from baseline to each of the post-randomisation visits (post Visit 4) up to and including the end of 48-week double-blind treatment visit (Visit 17) will be used as secondary efficacy variables. The pre-bronchodilator measurement recorded at Visit 4 will be used as baseline FEV1. If the Visit 4 pre-bronchodilator measurement is missing, the last non-missing pre-bronchodilator value before Visit 4 will be used as baseline instead.

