### **8.5 Methods for statistical analyses**

The analysis of the primary and secondary endpoints will include all data captured during the 48-week treatment period regardless of whether study treatment was prematurely discontinued, or delayed, and/or irrespective of protocol adherence.

To control the type I error rate, a testing strategy will be applied to the primary (annual asthma exacerbation rate) and 2 key secondary endpoints (the change in FEV1 and asthma symptom score from baseline to Week 48, respectively) for patients with baseline blood eosinophil counts  $\geq 300/\mu\text{L}$  for benralizumab. The testing strategy will be according to the following gate keeping procedure:

*Step 1:* Perform the test of annual asthma exacerbation rate (benralizumab vs. placebo) at the family wise error rate (FWER) of 0.05. If the p-value is less than 0.05, then proceed to Step 2; otherwise no null hypothesis is rejected.

*Step 2:* Test the 2 key secondary endpoints at the FWER of 0.05 using a Holm Procedure (Holm 1979).

Demography and baseline characteristics will be summarized by treatment group for the full analysis set. In the event that there are major differences between the full analysis set and safety analysis set, these summaries will also be repeated for the safety analysis set.

Additional analyses assessing the impact of Cases of Civil Crisis, Natural Disaster, or Public Health Crisis (e.g. SARS-CoV-2) may be included in the SAP.

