### **8.5.2 Analysis of the secondary variable(s)**

#### **8.5.2.1 Analysis methods for secondary efficacy variables**

Key secondary efficacy endpoints in this study are:

- Change from baseline in pre-bronchodilator FEV1 at Week 48
- Change from baseline in asthma symptom total score at Week 48

Other secondary efficacy endpoints include

- Proportion of patients with  $\geq 1$  asthma exacerbation
- Time to the first asthma exacerbation

- Annual rate of asthma exacerbations that are associated with an emergency room/urgent care visit or a hospitalization
- Change from baseline in total rescue medication use (average puffs/day)
- Change from baseline in morning and evening PEF at Week 48
- Change from baseline in asthma symptom day time/night time scores at Week 48
- Change from baseline in number of nights with awakening due to asthma and requiring rescue medication
- ACQ-6
- SGRQ

All the secondary efficacy endpoints will be analysed in patients with baseline blood eosinophil counts  $\geq 300/\mu\text{L}$ . In addition, the 2 key secondary efficacy endpoints will be analysed in patients with baseline blood eosinophil counts  $< 150/\mu\text{L}$ ,  $< 300/\mu\text{L}$ ,  $150\text{-}299/\mu\text{L}$ ,  $300\text{-}449/\mu\text{L}$  and  $\geq 450/\mu\text{L}$  separately.

Change from baseline in pre-bronchodilator FEV1 at Week 48 will be compared between the benralizumab group and placebo using a repeated measures analysis on patients with a baseline pre-bronchodilator FEV1 and at least 1 post-randomisation pre-bronchodilator FEV1 in the full analysis set. The dependent variable will be the change from baseline in pre-bronchodilator FEV1 at post-baseline protocol-specified visits (up to the EOT Visit). Treatment group will be fitted as the explanatory variable, and region (China/non-China), baseline pre-bronchodilator FEV1, visit, the interaction term of visit and treatment, and the use of maintenance oral corticosteroids (yes/no) will be fitted as covariates. Visit will be fitted as a categorical variable, and the variance-covariance matrix will be assumed to be unstructured. If the procedure does not converge then a compound symmetric variance-covariance matrix will be used instead. The model is:

*Change in FEV1 = Treatment group + baseline FEV1 + region + maintenance oral corticosteroids + visit + treatment \* visit*

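### Patients who stop IP early and choose monthly phone follow-up will have no Week 48 FEV1, and the protocol does not say whether they continue the diary

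*Supplement*

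**What the plan says.** Section 3.9.1 has every patient who stops IP return for a premature discontinuation (IPD) visit within 8 weeks +7 days of the last dose. At that visit the patient is encouraged to "complete all subsequent study visits, procedures and assessments or alternatively agree to be contacted by phone calls at monthly intervals". The second option is that patients "alternatively agree to be contacted by phone calls at monthly intervals in order to collect AEs/SAEs, changes in concomitant medication", and also health care use and exacerbations. Spirometry, the diary, ACQ-6 and SGRQ are not on that list.

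Section 8.5 states that the primary and secondary analyses "will include all data captured during the 48-week treatment period regardless of whether study treatment was prematurely discontinued". Two key secondary endpoints are tested by Holm's procedure once the primary test succeeds. For pre-bronchodilator FEV1, section 8.4.1.4 says "the change from baseline to Week 48 is included in the testing strategy", and section 8.5.2.1 models it "at post-baseline protocol-specified visits (up to the EOT Visit". The other is "Change from baseline in asthma symptom total score at Week 48", which comes from the Asthma Daily Diary.

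On the ePRO device, section 4.2 says: "Patients will return the ePRO device on EOT or IPD visit (for patients who are not willing to continue to participation in the study". Section 8.5.4 plans sensitivity analyses under different missing-data assumptions, including missing not at random, for the primary and key secondary endpoints. Their details are left to the SAP, which is not among the documents reviewed.

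**The concern.** An analysis that uses data regardless of treatment discontinuation depends on those data being collected. For the primary endpoint the protocol arranges this: the calls record exacerbations, and section 8.4.1.1 accordingly expects only loss to follow-up and withdrawal of consent to cause missing data. Nothing equivalent is written for the key secondary endpoints. A patient who remains in follow-up and gives full exacerbation data can still have no Week 48 FEV1, because the only alternative offered to full attendance is a phone call.

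In the main analysis, the repeated-measures model implicitly fills that gap from the patient's own earlier values, largely recorded under drug, and from patients in the same arm, most of whom presumably stayed on IP. If benefit wanes after stopping, benralizumab patients in this group are credited with benefit they no longer have. The effect estimated is then closer to an on-treatment effect than to the intention-to-treat effect described in sections 8.3 and 8.5.

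**Working it through.** The point rests mainly on reading the sections together. The protocol states no figure for it that could be reproduced.

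**Which endpoints the calls can supply**
- Exacerbations: yes, listed in 3.9.1.
- Pre-bronchodilator FEV1: no. Section 5.1.2 has it measured by spirometry at the study centre.
- Asthma symptom total score: not stated. It is recorded at home on the device, and section 5.3.2.1 runs the diary to the morning of Visit 17. Section 4.2 requires return of the device at IPD only from patients unwilling to continue, so phone-follow-up patients are not told to return it. But 3.9.1 offers calls in place of later procedures and assessments, does not list the diary, and the diary's end point is a visit these patients do not attend.

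**Whether the IPD visit stands in for Week 48**
- Doses fall at Weeks 0, 4, 8, 16, 24, 32 and 40.
- A patient whose last dose is at Week 32 has an IPD visit by Week 32 + 8 = 40, plus 7 days, so by Week 41 at the latest. This is 7 weeks before Week 48, and earlier stoppers are further away.
- The window reaches Week 48 only when the last dose was at Week 40, and such a patient has no scheduled dose left to miss.

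So the IPD visit supplies a late value for the model but not, in general, a Week 48 value.

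**Size, as an illustration**

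The only input from the documents is 444 patients (222 per arm) in the stratum with eosinophils of at least 300/µL. Assumed inputs are the share stopping IP, d = 5-15%, and the share of those choosing calls, s = 50%.

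Share missing Week 48 FEV1: m = d × s.
- Low: 0.05 × 0.5 = 2.5%; 444 × 0.025 = 11 patients.
- High: 0.15 × 0.5 = 7.5%; 444 × 0.075 = 33 patients.

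Let Δ be the on-treatment effect. Suppose the effect is wholly lost after stopping, the model predicts phone-only benralizumab patients as if still on drug, and stopping placebo changes nothing. The true treatment-policy effect is then (1 − d)Δ, the model gives (1 − d + m)Δ, and the excess is mΔ:
- 2.5% to 7.5% of Δ.
- Relative to the treatment-policy effect, m/(1 − d): 0.025/0.95 = 2.6% to 0.075/0.85 = 8.8%.

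Letting s run from 25% to 100% widens this:
- d = 5%, s = 25%: m = 1.25%, about 6 patients, 0.0125/0.95 = 1.3% of the treatment-policy effect.
- d = 15%, s = 100%: m = 15%, about 67 patients, 0.15/0.85 = 17.6%.

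The loss of precision is minor. For a comparison of means with 90% power at 222 per arm (an assumption, since the stated power concerns the primary endpoint), power with a share m missing is Φ(3.242√(1 − m) − 1.960). This gives 89.3% at m = 2.5% and 87.7% at m = 7.5%.

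**The case against.** Several counter-arguments have force.

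- **Sensitivity analyses are planned.** Section 8.5.4 covers both key secondary endpoints, includes missing-not-at-random assumptions and multiple imputation, and so addresses this very bias. That stands, and it limits the weight of the point. These analyses vary assumptions, however. They do not supply the measurements, and the Holm test is applied to the main model.
- **The diary may well continue.** A reader might infer that phone-only patients lose both key secondary endpoints. The text does not support that, because device return at IPD is tied to unwillingness to continue and no section stops the diary for patients on calls. What remains is an omission to clarify.
- **There is no contradiction with section 8.5.** A reader might take that section as promising complete Week 48 data. It says only that captured data will be used, and the restriction on sources of missing data in 8.4.1.1 is expressly for the primary analysis.
- **Full attendance is already the first request** in sections 3.9.1 and 8.4.1.1, and patients on calls have chosen not to attend. This is true, but a patient who declines every remaining visit may still accept one, and the protocol does not ask.
- **The bias is not as simple as drawn.** The unstructured model conditions on each patient's own earlier values. These should include IPD spirometry, since section 6.6.1 lets pregnant patients skip it there and so implies that others have it. Placebo stoppers are missing too. This makes the figures above closer to an upper bound for their assumed rates than to an expectation.

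**Conclusion.** The point holds for FEV1. Patients who stop IP early and take phone follow-up will lack the Week 48 value of a Holm-tested endpoint, and the main model must extrapolate it. For the symptom score, the protocol is silent on whether collection continues. The primary endpoint is unaffected.

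The likely size is modest: about 11-33 of 444 patients and 2.5-7.5% of the on-treatment effect, if 5-15% stop, half choose calls and the effect is fully lost. None of those rates is in the documents. Favouring benralizumab depends on benefit waning after stopping and on placebo patients being unchanged by it. Nothing here shows that a Holm-tested conclusion would change. This is a gap in data collection that can be closed cheaply, not a flaw that invalidates the analysis.

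**What to change.** In section 3.9.1, keep full attendance as the first request. For patients who choose phone follow-up, also ask them to:
- attend the already scheduled Visit 17 (Week 48) for pre-bronchodilator spirometry;
- continue the daily diary and the questionnaires on the device they already hold, to Week 48.

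In section 4.2, state that phone-follow-up patients keep the device until then.

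The change concerns data collection only. It costs protocol and consent wording, one existing visit and continued device use for a small number of patients. The downside is slight extra burden, and some patients may still decline, so the analyses in section 8.5.4 remain necessary.

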### **3.10 Criteria for withdrawal**

#### **3.10.1 Screen failures**

Screening failures are patients who do not fulfil the eligibility criteria for the study, and therefore must not be randomised. These patients should have the reason for study withdrawal recorded in eCRF as ‘Screen failure’ (the potential patient who does not meet one or more criteria required for participation in a trial, this reason for study withdrawal is only valid for not randomised patients). No further study related follow-up of these patients is required.

‘Failure to meet randomisation criteria’ should be selected for an indication that the patient has been unable to fulfil/satisfy the criteria required for assignment into a randomised group (it is only applicable for patient found not meeting criteria after randomisation).

#### **3.10.2 Withdrawal due to recruitment completion in a randomisation stratum**

When a specific stratum is full, patients in completed stratum will not be randomised and will be withdrawn from the study. The reason of the withdrawal should be documented in the source and eCRF as ‘development of study-specific withdrawal criteria’. As with screen failures, no further study related follow-up of these patients is required.

Strata closure process:

- 1 The eosinophil <300/ $\mu$ L stratum will be closed to all the patients from China when the total number of Chinese patients in the stratum reaches approximately 166.
- 2 The eosinophil <300/ $\mu$ L stratum will be closed to the patients from all countries when the total number of patients in the stratum reaches approximately 222.
- 3 The whole study will be closed for recruitment when the total number of patients in the eosinophil  $\geq$ 300/ $\mu$ L stratum reaches approximately 444, with at least 70% Chinese patients in the stratum.

### **3.10.3 Withdrawal of the informed consent/assent**

Patients are free to withdraw from the study at any time (IP and assessments), without prejudice to further treatment.

A patient who withdraws consent, and assent when applicable, will always be asked about the reason(s) and the presence of any adverse events (AE). The Investigator will follow up AEs outside of the clinical study. The patient will return electronic PRO (ePRO) devices if applicable. The enrolment/randomisation code of the withdrawn patient cannot be reused.

If patient agrees, he/she will be asked to return to the study centre and complete procedures described for the IPD (Premature IP Discontinuation) visit. For patients who are not willing to continue to participate in the study, he/she will complete IPD within 8 weeks +7 days after the last dose of IP and Follow-up visit within 16 weeks  $\pm$ 7 days after the last dose of IP.

### **3.10.4 Withdrawal of informed consent/assent for donated biological samples**

If a patient withdraws consent, and assent when applicable, to the use of donated biological samples, the samples will be disposed of/destroyed, and the action documented. If samples are already analysed, AstraZeneca is not obliged to destroy the results of this research.

As collection of the biological samples is an integral part of the study, then the patient is withdrawn from further study participation.

The Principal Investigator or designee:

- Ensures patients' withdrawal of informed consent, and assent when applicable, for the use of donated samples is notified immediately to AstraZeneca.
- Ensures that biological samples from that patient, if stored at the study centre, are immediately identified, disposed of /destroyed, and the action documented.
- Ensures the central laboratory (ies) holding the samples is/are informed about the withdrawn consent, and assent when applicable immediately and that samples are disposed/destroyed.
- Ensures that the patient and AstraZeneca are informed about the sample disposal.

AstraZeneca ensures the central laboratory(ies) holding the samples is/are informed about the withdrawn consent, and assent when applicable immediately and that samples are disposed of/destroyed and the action documented and returned to the study centre.

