### **8.3.2 Full analysis set**

All patients who were randomised and received any IP will be included in the full analysis set, irrespective of their protocol adherence and continued participation in the study. Patients will be analysed according to their randomised treatment, irrespective of whether or not they have prematurely discontinued, according to the ITT principle. Patients who withdraw consent, and assent when applicable, to participate in the study will be included up to the date of their study termination.

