#### **8.4.1.1 Exacerbation rate**

The annual asthma exacerbation rate will be used as the primary efficacy variable.

An asthma exacerbation is defined in Section 5.1.1.

In order to calculate the number of exacerbations experienced by a patient during the 48-week double-blind treatment period, the following rule will be applied.

The start of an exacerbation is defined as the start date of systemic corticosteroids, or the start date of a temporary increase in a stable oral corticosteroid background dose, or that start date of hospital admission, whichever occurs earlier. The end date is defined as the last day of systemic corticosteroids or the last day of a temporary increase in a stable oral corticosteroid background dose, or the date of discharge from a hospital, whichever occurs later. In the

primary analysis, the number of exacerbations observed for a patient during the 48-week double-blind treatment period will be used as response variable.

Additional systemic corticosteroid treatments, emergency room/urgent care visits requiring use of systemic corticosteroids, or inpatient hospitalization due to asthma occurring during an exacerbation should not be regarded as a new exacerbation. In order to be counted for as a new exacerbation it must be preceded by at least 7 days in which neither criterion is fulfilled.

The primary analysis will include all available data including data collected after treatment discontinuation. Subjects will be encouraged to continue to undergo applicable study related visits/procedures for the full 48-week treatment period even after premature discontinuation of IP. Consequently, subjects lost to follow-up and subjects who withdraw their consent/assent will be the only source of missing information for the primary analysis. Maximum follow-up time for a patient during the treatment period is approximately 48 weeks; defined as the time from randomisation to the date of Visit 17. For a patient lost to follow-up or withdraw consent/assent, follow-up time will be defined as the time from randomisation to the time point after which an exacerbation could not be assessed.

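### Withdrawing consent to sample use alone ends all follow-up of a randomised patient, although exacerbations and adverse events can be collected without samples

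*Supplement*

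**What the plan says.** Protocol Section 3.10.4 applies when a patient withdraws consent, or assent, "to the use of donated biological samples, the samples will be disposed of/destroyed, and the action documented". The consequence is stated in one sentence: "As collection of the biological samples is an integral part of the study, then the patient is withdrawn from further study participation". The section does not separate randomised from unrandomised patients, or one kind of sample use from another. Results already obtained need not be destroyed. Sections 3.10.2 and 3.10.5 each name the reason to enter in the eCRF; Section 3.10.4 names none. Withdrawal from the study as a whole has its own section, 3.10.3.

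Section 3.9.1 deals with patients who stop investigational product early. They are encouraged to complete the remaining visits or, failing that, to "agree to be contacted by phone calls at monthly intervals in order to collect AEs/SAEs, changes in concomitant medication, health care utilisation". The same sentence goes on to list exacerbations. Section 3.4 likewise encourages patients randomised in error to stay under follow-up, whatever is decided about treatment.

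For the primary endpoint, Section 8.4.1.1 says: "The primary analysis will include all available data including data collected after treatment discontinuation". It then states that "subjects lost to follow-up and subjects who withdraw their consent/assent will be the only source of missing information for the primary analysis". For those patients "follow-up time will be defined as the time from randomisation to the time point after which an exacerbation could not be assessed". Section 8.3.2 adds: "Patients who withdraw consent, and assent when applicable, to participate in the study will be included up to the date of their study termination".

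**The concern.** The event in Section 3.10.4 is an objection to the use of samples. The consequence is the end of all observation. A randomised patient who would have gone on answering questions about steroid courses, emergency visits, hospital stays and adverse events is no longer asked.

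This runs against the aim of the primary analysis, which is to follow randomised patients for the full 48 weeks whether or not they stay on treatment. The lost time is avoidable, because the protocol already has a route that collects these data without a sample. It may also be informative: a patient could object to sampling for reasons connected with tolerability or with confidence in the treatment. The documents neither show nor exclude this. Because no separate eCRF reason is named, these cases may also be hard to tell apart from full consent withdrawal when the missing-data sensitivity analyses of Section 8.5.4 are run.

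**Working it through.** **Do the outcomes need a sample?** Section 5.1.1 defines an exacerbation by systemic corticosteroid use, an emergency or urgent care visit, or hospitalisation. None of these needs a study sample, and neither does reporting an adverse event. Membership of the primary population rests on the eosinophil count at Visit 1, before randomisation, and existing results may be kept.

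**Does another section restore the follow-up?** Section 3.10.3 asks patients who withdraw consent, if they agree, for a discontinuation visit within 8 weeks and a follow-up visit within 16 weeks of the last dose. Even if that applied here, a patient whose last dose was at Week 8 would be last seen by about Week 24 (8 + 16), not Week 48. No other section overrides 3.10.4.

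**How many patients?** The documents give no frequency. Assumed range: 1% × 444 = 4.4 and 3% × 444 = 13.3, so about 4 to 13 patients in the primary population. For one patient leaving at Week 8, the unobserved share is (48 − 8)/48 = 83%. That is an example, not an expected value.

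**What does it cost in power?** The plan's 222 per arm for about 90% power cannot be reproduced, because the effect size and dispersion are redacted. As an illustration, take a two-sided 5% level, t = 336/365.25 = 0.920 year, and a placebo rate r0 = 0.88 per year. The rate appears only in the amendment history and is used here as an assumption. The negative binomial approximation is

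n per arm = (1.960 + 1.282)² × [1/(t·r0) + 1/(t·r0·RR) + 2k] / (ln RR)².

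The pairs of rate ratio RR and dispersion k that give 222 are (0.55, 2.04), (0.60, 1.11) and (0.65, 0.39). Check for RR 0.60: 10.507 × (1.235 + 2.059 + 2.22)/0.2609 = 222.

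Now let a fraction f in each arm leave at time T. With m the arm's rate and g(T) = mT/(1 + k·m·T), the information per arm is 222 × [(1 − f)·g(t) + f·g(T)]. Then SE = √(1/I0 + 1/I1), and power = Φ(|ln RR|/SE − 1.960).

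| f | Leave at day 0 | Leave at mid-treatment (range over the three pairs) |
|---|---|---|
| 0% | 90.0% | 90.0% |
| 1% | 89.71% | 89.87% to 89.91% |
| 2% | 89.42% | 89.74% to 89.82% |
| 5% | 88.48% | 89.35% to 89.54% |

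The day-0 column can be checked by hand. Information scales by (1 − f), so at 5% power is Φ(3.2415 × √0.95 − 1.960) = Φ(1.199) = 88.5%. These figures assume equal, non-informative withdrawal in both arms. They measure lost information, not bias.

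**The case against.** The strongest defence is that sampling really is integral here. The retained samples may be re-analysed only for their original purpose (Sections 5.3.5 and 5.3.6). The remaining testing includes central safety chemistry, haematology and urinalysis (Section 5.2.4), the pregnancy test before each dose (Section 7.4), and the pharmacokinetic, immunogenicity and eosinophil objectives. A patient who refuses sample use may therefore be refusing core safety procedures. This stands as far as it concerns continued treatment. It does not explain why exacerbations and adverse events should stop being recorded in a patient who agrees to report them.

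Four stronger readings are tempting, and the documents do not support them.

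- **Sections 3.9.1 and 3.10.4 contradict each other.** They do not. The first governs patients who stop treatment while still consenting to the study, the second those who withdraw sample consent. Both can be followed. Section 3.9.1 shows only that a sample-free route exists.
- **Section 3.10.4 creates a cause of missing data that Section 8.4.1.1 does not declare.** That section speaks of withdrawal of consent or assent without qualification, so withdrawal of sample consent can be read as included. The text is unclear rather than wrong.
- **Collected data are thrown away.** They are kept up to study termination, and the follow-up time in the offset is shortened to match.
- **The trial loses meaningful power.** The table above shows otherwise.

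Section 8.5.4 already plans sensitivity analyses that allow for data missing not at random. They help with interpretation but do not recover the observations.

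**Conclusion.** The point holds as a matter of retention. Section 3.10.4 gives an objection to sample use the effect of a full withdrawal, and so stops collection of exacerbations and adverse events that could have continued by an existing route. The number affected is unknown and probably small; the 1% to 3% is an assumption. On assumed design inputs the power cost is 0.1 to 0.3 points at 1% withdrawn and 0.5 to 1.5 points at 5%. The case rests on missing data that are avoidable and may be informative. That they are informative is a possibility, not something the documents show.

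**What to change.** Amend Section 3.10.4 so that a randomised patient who withdraws consent to sample use only is not taken out of follow-up for that reason alone. With the patient's agreement, offer the existing telephone follow-up of Section 3.9.1 (exacerbations, adverse events, concomitant medication and health care use, monthly) to the end of the planned period. Record this reason in the eCRF separately from full consent withdrawal. In Section 8.4.1.1, say how these patients are classified and that their follow-up time runs to the last contact at which exacerbations were assessed.

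The sponsor must also reconcile Section 3.10.4 with Section 3.9 and with the required safety and pregnancy testing, as regards investigational product. No rule on dosing is proposed here.

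The cost is a short amendment, matching consent-form wording and an eCRF entry. A few patients will have no later pharmacokinetic, antibody, eosinophil or safety laboratory data. Telephone contact will not supply their spirometry, so it does not recover the Week 48 FEV1 value.
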